## **Study population and methods**

### **Design**

A randomized open label, interventional study in 60 patients investigating if treatment with zoledronic acid prevents bone loss after denosumab treatment when administrated six (6-month group, n=20) or nine months (n=20, 9-month

group) after last injection of denosumab or when bone turnover is increased (n=20, observation group). Forty patients will be allocated to the two intervention groups and 20 patients will be followed without treatment for up to 12 months after the last denosumab treatment. The patients in the observation group and the nine months group will be monitored monthly and if p-carboxy-terminal collagen crosslinks (p-CTX) increases above 1.26µg/l (50% above the normal range for postmenopausal women and elderly men) infusion of zoledronic acid will be administered. Furthermore, a DXA scan (lumbar spine and hip sites) will be performed after three months in the observation group. If BMD has decreased more than 5% at the lumbar spine or total hip, infusion of zoledronic acid will be administered. Finally, if a patient in the 9 months group or the in the observation group suffers an osteoporotic clinical vertebral or hip fracture, infusion of zoledronic acid will be administered.

The patients will be given a single infusion of zoledronic acid as the increase in bone turnover seen after stopping denosumab seems most prominent in the first year [12]. The patients will be monitored with DXA 6, 12 and 24 months after the infusion of zoledronic acid. Zoledronic acid will be re-administered if BMD has decreased more than 5% at the lumbar spine, total hip or femoral neck.

If p-CTX increases above 1.26 µg/l during the 2nd year a second infusion of zoledronic acid will be administered.

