### Investigations

*Bone turnover markers:* Biochemical markers of bone turnover are s-bone alkaline phosphatase (s-BSAP), p-osteocalcin, p-PINP and p-CTX. The samples will be collected in peripheral blood samples in the morning (7:30–10:45 a.m.) after a minimum of eight hours of fasting, then centrifuged at 400 rpm at five degrees Celsius for ten minutes and stored at -80 degrees Celsius. P-CTX, p-osteocalcin and p-PINP will be analyzed on EDTA plasma using ELISA (Cobas 6000 immunoassay analyser, Roche Diagnostics GmbH) and BASP on serum using immunochemical reaction (ISYS). The samples will be analysed in a batch at the Department of Biochemistry, Aarhus University Hospital to reduce the analytical variation. The precision is  $\pm 7.4\%$  at 32  $\mu\text{g/l}$  (95% CI),  $\pm 10\%$  at 0.30  $\mu\text{g/l}$ ,  $\pm 6\%$  at 18  $\mu\text{g/l}$  and  $\pm 20\%$  at 44.4  $\mu\text{g/l}$  for p-PINP, p-CTX, p-osteocalcin and s-BSAP, respectively. If the results of any of the blood samples are below or above the detection range, we will use the lowest or highest detectable value, respectively. The BTMs will be measured at every clinical visit. If the specified p-CTX level is reached before month three (nine-months group) or month six (observation group) zoledronic acid will be administered.

*Biochemistry:* Markers of diseases affecting bone metabolism (calcium, phosphate, magnesium, 25-OH-vitamin D, PTH, creatinine, alkaline phosphatase, TSH). The samples will be analyzed at the Department of Biochemistry, Aarhus University Hospital.

*Bone mass:* Areal bone mineral density (aBMD) ( $\text{g/cm}^2$ ) of the lumbar spine (L1-L4) and hip (left) will be measured using a Hologic Discovery scanner (Hologic, Inc., Waltham, MA, USA). The right hip was scanned in case of prosthesis at the left hip. All participants were examined on the same DXA scanner throughout the trial. Incident vertebral fractures will be investigated using the vertebral fracture assessment (VFA) tool on the Hologic Discovery scanner. Lumbar spine trabecular bone score (TBS) will be measured using the TBS iNsight software, version 2.1.0.0 (Medimaps, Merignac, France).

*Bone quality:* Bone microarchitecture and estimated bone strength will be assessed by a high-resolution peripheral quantitative computed tomography (HR-pQCT) scan of the distal radius and tibia.

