*Treatment:* An intravenous infusion of 5 mg zoledronic acid will be administered at study day 0 (6-months group), at month three (9-months group), or depending on increase in p-CTX, decrease in BMD, or the occurrence of an osteoporotic clinical vertebral or hip fracture, but no later than at month 6 (observation group). The patients will be monitored with DXA 6, 12 and 24 months after the infusion of zoledronic acid. Zoledronic acid will be re-administered if BMD has decreased more than 5% at the lumbar spine, total hip or femoral neck. If p-CTX increases above 1.26  $\mu\text{g/l}$  during the 2nd year a second infusion of zoledronic acid will be administered.

*Fracture history:* Participants will be questioned about incident fractures at months 12, 15, or x+12 and again at months 24, 27, or x+24. Information will be confirmed using discharge notes from hospitals.

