### **Statistical analysis and power calculation**

Baseline characteristics of the three groups will be presented using descriptive analysis and compared using ANOVA and post-hoc unpaired t-tests if ANOVA demonstrates differences between the groups. Changes in bone mineral density one year after the zoledronic acid infusion within groups will be investigated using paired-sample t-tests and compared with the changes reported after stopping denosumab after two years [12] for the three groups combined and individually using one-sample t-test. The proportion of patients who fails to maintain BMD will be compared between groups using chi-sq test. Changes in bone mineral density, HRpQCT measures and markers of bone turnover will be compared between groups using mixed model analysis. Exploratory analyses will include multiple regression analyses aiming at identifying baseline factors or changes occurring at three or six months, which affect the change in BMD one year after the zoledronic acid infusion. Factors included in this analysis will be gender, age, years of treatment with denosumab, baseline BMD, baseline bone turnover markers, change in bone turnover markers three and six months after the zoledronic acid infusion.

Based on a previous study a 5% decrease in lumbar spine BMD can be expected during the first year after discontinuation with a 3% standard deviation [12]. The hypothesis is that treatment with zoledronic acid can decrease this bone loss. Eighteen patients will be needed to demonstrate a bone loss  $\geq 2.5$  % using a paired-sample t-test with a power of 90% and level of significance of 5%. If the decrease is less than that BMD is maintained and the hypothesis can be accepted. To account for dropouts n is increased to 20 in each group. As comparisons between the different treatment regiments suggested in this protocol never have been done before, we cannot estimate differences between groups. However, the least significant change in lumbar spine BMD using DXA is 3%. The SD of lumbar spine BMD in our facility is 3% [18]. To be able to demonstrate a difference in change in lumbar spine BMD between the three groups equal to the least significant change using independent samples t-test we need 16 patients in each group with a standard

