deviation of 3%, power of 80% and significance level of 5%. Thus, the already planned 20 participants per group are sufficient to make meaningful exploratory analyses. New participants will be enrolled after four dropouts in total. Per-protocol analysis will be performed.

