### **Safety and ethical considerations**

Puncture of veins for blood sampling can result in a bruise and very rarely in infection. The DXA and HRpQCT examinations result in radiation doses of maximum 120 $\mu$ Sv and 24 $\mu$ Sv, respectively. This increases the risk of cancer by 0,0007% and the lifetime risk of cancer increases from 25% to 25.0007%. Known side effects to short-term treatment with zoledronic acid include flu-like symptoms that subside within 2-3 days. For a more detailed list of the known side effect see section 4,8 in the public assessment report of zoledronic acid by the Danish National Board of Health (<http://www.produktresume.dk/docushare/dsweb/View/Collection-124>).

It would have been more scientifically sound to include a placebo group in the study but we believe that it is already proven that patients in this group would lose most or all of the bone gained on denosumab therapy within a year why we believe it is more ethical to do an uncontrolled study.

As mentioned in the background there have been publications on patients who experienced vertebral and multiple vertebral fractures after stopping denosumab. These cases are rare and we aim to reduce this risk further for participants in the present study by monitoring patients bone turnover by monthly measurement of p-CTX, by performing DXA after three months in the observational group and by allowing treatment prior to schedule if bone turnover increases or bone

mass decreases significantly or if a patient suffers an osteoporotic clinical vertebral or hip fracture. We therefore believe that the risks associated with participating in this study are limited and we believe the potential gains from this study outweigh the risks.

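### The one-sample t-test against the published loss after stopping denosumab treats a sample mean as a known constant, so its error exceeds the nominal 5%, most of all with the groups pooled

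*Combined protocol and SAP*

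**What the plan says.** The section *Statistical analysis and power calculation* plans paired t-tests of the BMD change within groups one year after the infusion. It then has these changes "compared with the changes reported after stopping denosumab after two years [12] for the three groups combined and individually using one-sample t-test". From the same source it takes its planning value: "Based on a previous study a 5% decrease in lumbar spine BMD can be expected during the first year after discontinuation", with an SD of 3%. The hypothesis is that zoledronic acid reduces that loss. A mean loss of 2.5% is the margin, with the rule "If the decrease is less than that BMD is maintained and the hypothesis can be accepted".

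No sample size, standard error or confidence interval is given for the reference mean, and nothing in the documents carries its uncertainty into the test. The 5% level appears only in the two sample-size calculations. No level or sidedness is stated for the one-sample test.

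Under *Safety and ethical considerations* the authors explain the lack of a placebo arm: "we believe it is more ethical to do an uncontrolled study". Under *Design*, the observation arm is described thus: "20 patients will be followed without treatment for up to 12 months after the last denosumab treatment". The 6-month group is infused at baseline, so this means at most about six untreated months after baseline, and fewer if a treatment trigger is met.

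**The concern.** A one-sample t-test is exact when the comparison value is a constant fixed in advance. Here the value is an estimate from another study's patients, and the plan itself attaches an SD to it. Leaving out its sampling error makes the standard error of the difference too small and the p-value too small. The pooled test suffers most, because the larger the trial sample, the greater the share of the true uncertainty that lies in the omitted part.

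This is the only planned one-year comparison with untreated loss, since no arm stays untreated for a year after baseline. The risk is a claim that patients lost less bone than untreated patients when they lost the same, made more often than the nominal level allows. The confidence interval for the trial's own mean change is not affected.

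**Working it through.** **Inputs from the plan.** n = 20 per group and 60 in total; reference lumbar spine loss 5%, SD 3%; facility SD 3%; margin 2.5%; nominal level 5%, taken as two-sided.

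**Assumed.** The number of reference patients, m, is not in the documents. I use 40 to 200, with 1000 as a near-negligible case, and equal SDs in the two studies.

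**The plan's own figures.** A paired t-test with standardised effect 2.5/3 = 0.833, two-sided 5% and 90% power needs n = 17.17, hence 18, as stated. The between-group figure of 16 per group also reproduces with the normal formula (17 with the t distribution). Neither calculation concerns the comparison with the published value.

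**Error rate.** With common SD s, the variance of the difference in means is s²(1/n + 1/m) = (s²/n)(1 + n/m). The one-sample test uses s²/n only. If the true means are equal, its statistic is distributed as sqrt(1+n/m) times t with n−1 df, so

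two-sided error = 2·P(t(n−1) > t(0.975, n−1)/sqrt(1+n/m)).

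- n=20, m=40: 2.093/sqrt(1.5) = 1.709, giving 10.4%.
- n=60, m=40: 2.001/sqrt(2.5) = 1.266, giving 21.1%.

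| n | m=40 | m=100 | m=200 | m=1000 |
|---|---|---|---|---|
| 20 (one group) | 10.4% | 7.1% | 6.1% | 5.2% |
| 60 (pooled) | 21.1% | 11.9% | 8.4% | 5.7% |
| 18 (one group, after dropout) | 9.8% | 6.9% | 5.9% | 5.2% |
| 56 (pooled, four dropouts) | 20.1% | 11.4% | 8.2% | 5.6% |

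The last two rows reflect the dropout rule: "New participants will be enrolled after four dropouts in total. Per-protocol analysis will be performed". In the benefit direction alone (nominal 2.5%), for m = 40 to 200, the error is 5.2% to 3.0% per group and 10.5% to 4.2% pooled. The SD cancels, so the table holds at any BMD site where the two studies have similar SDs. If the reference SD is 0.75 to 1.5 times the trial SD, then at m=100 the error is 6.2% to 9.8% per group and 8.9% to 19.7% pooled. Keeping the error at or below 6% would take about 210 reference patients for one group and about 676 for the pooled test.

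**Where significance changes.** Lumbar spine, SD 3%, benchmark 5%. The threshold is 5 minus the 95% half-width.

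- One-sample: 2.093×3/sqrt(20) = 1.40, so an observed loss below 3.60% is significant per group; 2.001×3/sqrt(60) = 0.77, so below 4.23% pooled.
- Welch per group: half-width 1.66 (m=40) or 1.46 (m=200), so below 3.34% or 3.54%.
- Welch pooled: half-width 1.22 or 0.88, so below 3.78% or 4.12%.

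An observed loss of 2.5% is significant under both tests. At n=20, m=40 it stays so under Welch while both SDs are below 4.5% (below 5.3% for the one-sample test).

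**How often the tests disagree.** Chance that the one-sample test claims benefit and Welch does not, m = 40 to 200, by simulation with 1,000,000 trials per cell:

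| True difference from reference | One group | Pooled |
|---|---|---|
| 1 point | 10.6% to 2.5% | 28.0% to 8.4% |
| 2.5 points | 6.3% to 0.9% | 1.6% to under 0.1% |
| 5 points | none | none |

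In the simulation Welch's two-sided error was 4.97% to 5.04%.

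**The case against.** The strongest reply is that the reported change is meant as a fixed benchmark. For the null hypothesis that the trial mean equals exactly 5%, the one-sample test has its nominal level. That is correct, but the plan does not declare a fixed benchmark. It compares with the changes reported in a study, and its hypothesis is that treatment reduces the loss that follows stopping denosumab. For that conclusion the uncertainty of the reference belongs in the test.

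Second, the practical reach is small. The co-primary endpoints are the six-month lumbar spine change and the failure proportion, and neither uses this test. The range of observed losses in which the two tests disagree is only about 0.05 to 0.44 percentage points wide, and all of it lies above 3%. The plan puts the least significant change at 3% and counts a lumbar spine loss of 3% or more as failure in a patient, so a mean loss in that range would hardly be presented as maintained BMD. This stands. What remains exposed is a claim of some reduction in loss, mainly from the pooled test.

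Third, the size depends on an m that the documents do not give. This also stands: only the direction and the ordering, pooled above single group, follow without it.

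Fourth, Welch does not make a historical comparison a fair one. Differences in population and timing may matter more than the choice of test. That is true, and it is a reason to state those limits; it does not justify leaving the standard error too small.

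**Conclusion.** The concern holds. As written, the comparison omits the sampling error of the published mean, and if the true means are equal its error is above a nominal 5% for any finite reference sample. For 40 to 200 reference patients and equal SDs it is 10.4% to 6.1% per group and 21.1% to 8.4% pooled; with 1000 reference patients it would be 5.2% and 5.7%. The direction is certain under the reading that untreated loss is the comparator. The size rests on the assumed m and on similar SDs.

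The consequence is moderate. A clear success by the plan's 2.5% criterion would not be overturned at SD 3%. A modest effect could be called significant when the evidence does not support it. This should be corrected, but it does not threaten the co-primary analyses.

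**What to change.** Replace the one-sample t-test with a two-sample Welch comparison from summary statistics, using the mean, SD or SE, and n published in reference [12]. Report the difference with its 95% CI, per group and pooled, and label it a historical comparison. For any BMD site where that paper prints no SD or SE and n, show the trial's mean change with its 95% CI beside the published mean, without a p-value. If a fixed benchmark is what is meant, the plan should say so and limit the conclusion to that value.

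State two limits that Welch does not remove:

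- **Population.** The title of [12] names postmenopausal women with low bone mass. This trial also admits men and excludes T-scores below −2.5.
- **Timing.** One year after infusion falls 12 months after baseline in the 6-month group, up to 3+12 = 15 in the 9-month group and up to 6+12 = 18 in the observation group. The benchmark is a first-year loss.

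The cost is a change of wording and a few figures from a paper already cited. Endpoints, scans and patient numbers stay as planned. The downside is that intervals for this difference become 4% to 18% wider per group and 13% to 57% wider pooled (m = 200 to 40), so small differences may lose significance.

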## **Aims**

To investigate if infusion of zoledronic acid can prevent increases in bone turnover and bone loss in patients previously treated with denosumab and if there is difference between infusing zoledronic acid at six or nine months after the last injection of denosumab or when bone turnover is increased. The reason for investigating different time points for the infusion of zoledronic acid is that if bone remodelling is strongly suppressed by the previous denosumab treatment, bisphosphonate may not adhere well enough to the bone surface to inhibit resorption once the effect of denosumab wears off. It has been demonstrated that some patients still have completely suppressed markers of bone turnover six months after the last injection but also that most patients have regained some resorptive activity three months later [12].

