#### **Co-primary endpoint**

- Change in lumbar spine BMD from baseline to 6 months after the zoledronic acid infusion.
- The proportion of patients who fails to maintain BMD (total hip, femoral neck and spine). Failure is defined as  $\geq 3$  % BMD loss at the lumbar spine or  $\geq 5$  % BMD loss at the femoral neck or total hip.

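### The failure co-primary is tested only between arms that all receive zoledronic acid, and the plan's two rules for maintained BMD are not linked

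*Combined protocol and SAP*

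**What the plan says.** The Aims section poses two questions. The first is prevention: "To investigate if infusion of zoledronic acid can prevent increases in bone turnover and bone loss in patients previously treated with denosumab". The second is whether the timing of the infusion matters.

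The Co-primary endpoint section lists two endpoints. One is change in lumbar spine BMD to 6 months after infusion. The other is "The proportion of patients who fails to maintain BMD (total hip, femoral neck and spine"), where a patient fails on losing 3% or more at the lumbar spine, or 5% or more at the femoral neck or total hip. No time point and no reference proportion are given for failure.

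Statistical analysis and power calculation gives this endpoint a single analysis: "The proportion of patients who fails to maintain BMD will be compared between groups using chi-sq test". For continuous BMD change it gives more: paired t-tests within groups, one-sample t-tests against the published change after stopping denosumab (groups combined and separately), and a mixed model between groups.

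The same section assumes that a "5% decrease in lumbar spine BMD can be expected during the first year after discontinuation with a 3% standard deviation". It sizes each arm to detect a mean loss of 2.5% with a paired t-test, then adds: "If the decrease is less than that BMD is maintained and the hypothesis can be accepted".

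Under Investigations (Treatment), the observation group is infused by month 6 at the latest, so all three arms are treated. Safety and ethical considerations describes the study as uncontrolled.

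**The concern.** A comparison between three treated arms can show that one timing is better than another. It cannot show that treatment prevents loss, because no arm supplies the untreated result. If all three arms had the same failure rate, the chi-square would give the same answer whether that rate was low or as high as expected without treatment. As written, the plan says nothing about how to read this co-primary when the arms are alike.

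The second difficulty is the word *maintained*. The sample-size text applies it to an arm whose mean spine loss is below 2.5%. The endpoint definition applies it to a patient, with cut-offs of 3% and 5%. Nothing says how the two relate or which governs the conclusion. The report could declare BMD maintained on the mean rule while a sizeable share of the same arm fails the other co-primary.

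**Working it through.** **Inputs.** Statistical analysis and power calculation: untreated first-year spine loss 5%, SD 3%; mean loss for the acceptance rule 2.5%; 20 patients per arm. Co-primary endpoint: spine failure at a loss of 3% or more. Assumptions made here: changes are normally distributed, and the 3% SD holds after zoledronic acid.

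**1. The plan's own figures.** Paired t-test, standardised effect 2.5/3 = 0.833, two-sided 5%, power 90%: n = 17.2, rounded up to 18, as stated (power 0.915 at 18). Between groups, normal approximation: 2 × (1.960 + 0.842)² × (3/3)² = 15.7, rounded up to 16, as stated. Both concern continuous spine BMD change. No calculation is given for the failure proportion.

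**2. What the chi-square can tell.** With 20 patients in each of three arms and equal true failure rates, the simulated rejection rate at the 5% level is:

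| True failure rate in all arms | Chi-square rejects |
|---|---|
| 16% | 4.4% |
| 43.4% | 4.9% |
| 74.8% | 5.2% |

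The test does not separate uniform success from uniform failure.

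**3. Spine failures implied by a mean loss m.** P(loss ≥ 3%) = Φ((m − 3)/SD). With SD 3%:

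| Mean loss m | (m − 3)/3 | Spine failures |
|---|---|---|
| 0% | −1.000 | 15.9% |
| 1% | −0.667 | 25.2% |
| 2% | −0.333 | 36.9% |
| 2.5% (acceptance boundary) | −0.167 | 43.4% |
| 5% (untreated assumption) | +0.667 | 74.8% |

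At the 2.5% boundary, SD 2% gives Φ(−0.25) = 40.1% and SD 4% gives Φ(−0.125) = 45.0%. At the untreated 5%, the same SDs give 84.1% and 69.1%.

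**4. The other reading of acceptance.** Suppose it means a non-significant paired t-test with 20 patients. The largest non-significant mean loss is 2.093 × 3/√20 = 1.40%. Spine failures are then Φ((1.40 − 3)/3) = 29.7%.

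**5. Hip sites.** These can only add failures. The documents give no hip means, SDs or correlations. With assumed mean hip loss of 0 to 2.5%, SD 2 to 3% and correlations of 0 to 0.6, the composite at the 2.5% spine boundary runs from 43.5% to 64%.

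**6. Is a within-arm estimate informative at 20?** Ten failures in 20 gives an exact 95% interval of 27% to 73%, which lies below 74.8%. If the true rate is 43.4%, the chance of 10 or fewer failures is 0.795. If mean loss is zero (15.9% failures), it exceeds 0.99.

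**The case against.** The strongest reply is that prevention is already tested. The statistical section has paired t-tests and one-sample t-tests against the published change, by arm and combined. Timing is a stated aim, the chi-square suits it, and a plan need not test every aim with every endpoint. This stands, and it limits the point to one endpoint. A reader might infer that the trial has no test of prevention; the documents do not support that.

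A reader might also infer that the two rules contradict each other. They do not. One concerns a group mean. The other is a per-patient cut-off, and its 3% matches the least significant change that the plan states for spine DXA. Even with no mean loss, 16% of patients would cross it. The fault is that one word covers two rules with no stated link.

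Third, 43% might be read as an expected failure rate. It is the limit of the literal rule, reached only when mean loss sits just under 2.5%. It borrows an SD that the plan states for loss after stopping denosumab and for spine BMD at the facility, not for change after zoledronic acid. The paired-test reading brings it down to about 30%.

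Last, it is tempting to add a pass mark: call an arm maintained if its upper limit is below 75%. That would not help. An arm with a true failure rate of 43.4% would pass about 80% of the time, and beating an untreated rate shows less loss, not maintenance.

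**Conclusion.** The point holds for the failure co-primary. Its only planned analysis addresses timing, so on the prevention aim this endpoint has no planned estimate, interval or reference value. The two uses of *maintained* are unlinked and can point in opposite directions for the same arm. Up to about 43% of patients could fail at the spine alone in an arm accepted under the literal rule, or about 30% under the significance-test reading. These figures rest on normality and on the 3% SD carrying over to treated patients. The range for SDs of 2% to 4% is narrow at the boundary, so the conclusion does not depend on that choice. The 75% reference is more sensitive (69% to 84%). It is also a one-year figure from discontinuation, so its fit depends on the time point chosen for failure.

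**What to change.** In Statistical analysis and power calculation:

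- Report the failure proportion for each arm, and for the arms combined, with an exact 95% confidence interval.
- State the time point. The Co-primary endpoint section gives none for failure, while Duration of study puts the primary endpoints at 12 months after infusion and the other co-primary is at 6 months.
- Set each proportion and interval against the roughly 75% spine failure implied by the plan's own 5% loss and 3% SD. This is a conservative reference for the composite, because hip failures can only raise the untreated rate. Word a favourable result as less loss than expected untreated, not as maintained BMD.
- Do not conclude that BMD is maintained from the 2.5% mean rule alone. Report it beside the arm's failure proportion and interval, and say how the two rules relate.
- Keep the chi-square, labelled as the timing comparison.

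No new patients, visits or measurements are needed. The cost is a little more analysis, and maintenance becomes harder to claim.

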#### **Secondary endpoints**

- Changes in total hip, femoral neck and lumbar spine BMD from baseline to one year after the zoledronic acid infusion.
- Changes in total hip, femoral neck and lumbar spine BMD from baseline to two years after the zoledronic acid infusion.
- Changes in trabecular bone volume fraction (bone volume/tissue volume, BV/TV) and cortical porosity measured by high-resolution peripheral quantitative computed tomography (HR-pQCT) scan at the radius and tibia from baseline to one year after the zoledronic acid infusion.
- Changes in p-CTX and p-procollagen type I N-terminal propeptide (p-PINP) from baseline to six months after the zoledronic acid infusion.
- Changes in p-CTX and p-PINP from baseline to 12 months after the zoledronic acid infusion.
- Morphometric vertebral fractures assessed by vertebral fracture assessment (VFA) one and two years after the zoledronic acid infusion.

---

 Electrochemiluminescence immunoassay (ECLIA) will be used.

 Reference range: Women 30-50 years: 0,04 - 0,59 µg/l. Women > 50 years: 0.03-0.83 µg/l. Men 30-50 years: 0,09 - 0,63 µg/l. Men 50-70 years: 0.04-0.84 µg/l. Men > 70 years: 0,08 – 1,05 µg/l.

 ECLIA will be used.

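### The plan gives conflicting times for the primary endpoints, and its between-group BMD changes cover unequal periods without showing how much loss occurred before infusion

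*Combined protocol and SAP*

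**What the plan says.** **Reading time.** Four places in the combined protocol and SAP bear on it.

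- Co-primary endpoint, first item: "Change in lumbar spine BMD from baseline to 6 months after the zoledronic acid infusion".
- Co-primary endpoint, second item: "The proportion of patients who fails to maintain BMD (total hip, femoral neck and spine"). Failure is a loss of at least 3% at the lumbar spine or at least 5% at either hip site. No time is attached.
- Secondary endpoints: "Changes in total hip, femoral neck and lumbar spine BMD from baseline to one year after the zoledronic acid infusion".
- Duration of study has the primary endpoints read 12 months after infusion. Statistical analysis and power calculation plans the within-group paired t-tests, and the one-sample comparison with the earlier discontinuation study, at one year after infusion.

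**Between-group comparison.** The statistical section states "Changes in bone mineral density, HRpQCT measures and markers of bone turnover will be compared between groups using mixed model analysis" and "The proportion of patients who fails to maintain BMD will be compared between groups using chi-sq test". It names no time axis, contrast or visit for the mixed model, and no separation of change before and after infusion. Under Investigations, infusion is at day 0 in the 6-month group, month 3 in the 9-month group, and no later than month 6 in the observation group. It comes earlier if a trigger is met in either delayed group. The study plan schedules a DXA at the planned infusion visit in every group: baseline, M3 and Mx.

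**Aim.** The Aims ask "if there is difference between infusing zoledronic acid at six or nine months after the last injection of denosumab". The reason given for varying the time is that, after strong suppression, "bisphosphonate may not adhere well enough to the bone surface to inhibit resorption once the effect of denosumab wears off".

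**The concern.** A co-primary endpoint needs one reading time and a test at that time. Here the lumbar spine change is primary at 6 months in one section and at 12 months in another, and the tests described are at the later time. Failure could be read at either time. Unless this is settled before analysis, the primary result can be chosen after the data are seen.

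The second matter is interpretation. Follow-up after infusion is equal in all groups but the start is a common baseline, so the delayed groups carry extra months, all of them before infusion. A worse result in a later group may reflect only bone lost during the wait. Similar results could combine more waiting loss with a better response after infusion. The total change alone does not say which, and the Aims raise both the timing question and a mechanism that acts after infusion.

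**Working it through.** **1. Reading times side by side**

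| Section | Lumbar spine BMD change | Failure proportion |
|---|---|---|
| Co-primary endpoint | 6 months after infusion | none stated |
| Duration of study | 12 months (all primary endpoints) | 12 months (all primary endpoints) |
| Secondary endpoints | one year, as secondary | not listed |
| Statistical analysis | paired and one-sample tests at one year | chi-square, no time stated |

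The first two rows cannot both hold for lumbar spine BMD. If the 6-month reading is primary, no within-group test is planned for it. If the 12-month reading is primary, it is also listed as secondary.

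**2. The plan's own sample sizes**

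- Within group: loss 2.5%, SD 3%, two-sided 5%, 90% power. The exact paired t-test gives n = 18 (power 91.5%; n = 17 gives 89.7%), matching the plan.
- Between groups: difference 3%, SD 3%, 80% power. The normal approximation gives 16 per group, matching the plan. The exact t-test gives 17 (power at 16 is 78.1%).

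Nothing below changes these.

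**3. Length of the periods compared** (wait plus time after infusion, in months)

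| Group | Wait | To the 6-month reading | To the 12-month reading |
|---|---|---|---|
| 6-month | 0 | 6 | 12 |
| 9-month | 3 | 9 | 15 |
| Observation | up to 6 | up to 12 | up to 18 |

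A trigger shortens the wait in the 9-month group as well.

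**4. Size of the waiting component**

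The statistical section expects that "a 5% decrease in lumbar spine BMD can be expected during the first year after discontinuation with a 3% standard deviation". Assume this loss is linear from baseline, the response after infusion is the same in every group, SD is 3% for each change, and n = 20 per group.

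- Gap against the 6-month group = yearly loss × wait / 12: 5 × 3/12 = 1.25 points; 5 × 6/12 = 2.5 points (upper bound).
- Against the 3-point difference used for sizing: 1.25/3 = 42%; 2.5/3 = 83%.
- Standard error = 3 × √(2/20) = 0.95.
- Two-sided 5% t-test (noncentral t, 38 df): significant in 25.0% and 72.8% of trials.
- If observation patients are infused at month 4 on average: 5 × 4/12 = 1.67 points, 40.2%.

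| Assumption varied | 3-month wait | 6-month wait |
|---|---|---|
| Loss 2.5% to 10% a year, SD 3% | 0.6 to 2.5 points; 10% to 73% | 1.25 to 5.0 points; 25% to over 99% |
| SD 4% to 2%, loss 5% a year | 16% to 49% | 49% to 97% |

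The lower end is plausible for the early months: the Aims note that some patients are still fully suppressed six months after the last injection.

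**5. Failure proportion**

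Using the lumbar spine criterion alone, with infusion halting loss, P(loss ≥ 3) for mean losses of 0, 1.25 and 2.5 and SD 3 is 15.9%, 28.0% and 43.4%. The three-group chi-square is then significant in 39.5% of trials, or 18.8% if the mean observation wait is 4 months.

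**6. What the gap means**

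Let r be yearly loss before infusion, s yearly loss after it and d the wait in months. At a common month 12 the gap is d(r − s)/12. With r = 5 and d = 6 this is 2.5 points if s = 0, 1.25 if s = 2.5, and 0 if s = 5. If infusion halts loss, the whole gap is a true cost of delay.

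**7. What a split at infusion can and cannot show**

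Suppose infusion halves loss equally in all groups, but untreated loss is 3.75 points in the first six months and 1.25 in the second. From infusion to 6 months, the 6-month group loses 3.75/2 = 1.875 and a patient infused at month 6 loses 1.25/2 = 0.625. The gap is 1.25 points (significant in 25%) with no difference in drug effect.

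**The case against.** The strongest reply is that change from a randomised baseline is the right measure for the timing aim. Bone lost while waiting is part of what a later infusion costs, and the adhesion argument is a rationale rather than the stated question. This stands. The baseline-anchored endpoint is legitimate and should stay.

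Three stronger readings are tempting, and the documents do not support them.

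- *That 25% and 73% are error rates.* Step 6 shows that if infusion halts loss they are the power to detect a real difference between strategies.
- *That the trial is unable to separate waiting loss from later response.* A DXA at infusion is scheduled in each group, bone markers are measured after infusion, and the exploratory regression uses marker change at three and six months after infusion. What is missing is a prespecified analysis, not the data.
- *That splitting at infusion isolates drug effect.* Step 7 shows that it does not, because the post-infusion periods fall at different phases of the rebound. Infusion in the observation group is also triggered by response.

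It is also fair to say that the plan calls the between-group analyses exploratory, that its sized test is within group, and that the 5% a year is for a full year and may not apply to the first three months. These points limit the weight of the second matter. They do not touch the conflicting reading times. The failure proportion is a co-primary endpoint compared between groups, and it has no time in its own definition.

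**Conclusion.** The reading time of the primary endpoints is contradictory as written and should be fixed. That conclusion rests on the text alone and needs no assumption.

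The unequal periods are real but are a matter of interpretation, not a flaw in the randomised comparison. Under linear loss of 5% a year, equal response after infusion, SD 3% and 20 per group, waiting alone accounts for 1.25 points in the 9-month group and up to 2.5 points in the observation group. At 2.5% to 10% a year the ranges are 0.6 to 2.5 and 1.25 to 5.0 points. This is large enough that a reader needs to see the waiting component reported beside the total. The within-group sample size is unaffected.

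**What to change.** 1. Reconcile Co-primary endpoint, Secondary endpoints, Duration of study and Statistical analysis. Set one primary reading time for lumbar spine BMD change and one for failure, and run the planned tests of each at that time.
2. Keep the baseline-anchored change as the between-group endpoint. State that it and the failure proportions compare whole strategies over unequal periods.
3. Add, as exploratory only, BMD change from baseline to infusion (zero by design in the 6-month group) and from infusion to 6 and 12 months, by group, using the DXA already scheduled at baseline, M3 and Mx. State its limits:
   - the post-infusion periods fall at different phases of the rebound, so a gap is not proof of a different drug effect;
   - infusion in the observation group is response-triggered, so that contrast is not purely randomised and is open to regression to the mean;
   - 9-month patients infused before M3 have no DXA scheduled at infusion, so say how they are handled;
   - HR-pQCT is done only at baseline and 12 months after infusion, so it cannot be split in the delayed groups.

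The cost is SAP wording and slightly more analysis, with no extra scans or patients. The downside is a low-powered contrast: 25% for a 1.25-point difference at SD 3% and 20 per group.
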